patients and 54,284 breaths from the REDvent cohort at CHLA), 28.7% of breaths had some form of asynchrony, with 63/65 (95.4%) patients demonstrating at least one episode of PVA. The predominant asynchrony subtypes were flow undershoot (13.8%), delayed termination (7.4%), premature termination (5.1%), and reverse trigger (1.9%). Double cycled breaths occurred 3% of the time (see below). In a mixed cohort of 74 children at Beatrix Children's Hospital that used sEMG, 33% of breaths had some form of asynchrony. The predominant asynchrony subtypes were ineffective trigger (68%) followed by delayed termination (19%). DC breaths occurred 4% of the time. In a mixed cohort of 62 children at St. Justine Children's hospital that used Edi, 27% of breaths had some form of asynchrony. The predominant asynchrony subtypes were trigger delay (9%), ineffective efforts (10%) and premature termination (4%). DC breaths occurred 1% of the time. There are high rates of PVA amongst ventilated children, with differences in PVA subtypes based on institution, technique of measurement of neural effort, and disease state. These findings underscore the need to have common operational definitions for PVA subtypes which can incorporate different methods to measure neural effort, with a diverse, heterogeneous sample of ventilated children from multiple institutions.

Double Cycle (DC) occurs in approximately 3% of breaths, with underlying asynchrony subtypes nearly equally split between Reverse Trigger and Premature

Termination/Flow Undershoot. A DC breath occurs when the ventilator delivers a second breath before the patient has fully exhaled. This is particularly injurious because it leads to very high tidal volumes and risk of volutrauma (strain), in addition to high transpulmonary pressure and barotrauma (stress).^{21,22,24,48-51,60} In the REDvent cohort, 3.0% of breaths were DC, with at least one DC breath occurring in 46/65 (70.8%) patients. The most common PVA associated with DC breaths was reverse trigger (52.5%). High patient effort with flow undershoot/premature termination was also very common (45.2%, combined for analysis), while auto trigger (1.2%) was rare. Rates of DC breaths were similar in cohorts from St. Justine (1%) and Groningen (4%), but the underlying PVA subtype was not characterized.

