Methods: On a high level, a spectral tensor is used as input to a Convolutional Neural Network (CNN) model, which generates predictions that show the likelihood of a breath having asynchrony, with a specific asynchrony subtype. CNN are widely used in computer vision tasks⁷³, which make them appropriate for this application. Our group has extensive experience with machine learning models in the ICU environment.⁷⁴⁻⁸⁰ The methods are based on analysis of three contiguous breaths, called a breath triplet with the breath of interest being the central breath (Figure 10). Breath triplets are generated from the two readily available clinical waveforms (flow spirometry and airway pressure). Each triplet is labeled with the asynchrony types associated with its central breath. A sliding Discrete Fourier Transform (DFT) is used to transform each of the waveforms of a triplet into two spectrograms: one with the power spectral density (PSD), which measures the energy of sinusoids in each channel, and another containing phase, which measures the angular shift of the sinusoids. This results in four spectral images for each triplet (Figure 10). Methods are employed to remove noise⁸¹ and the spectrograms are aggregated in a stack to create a 4-channel image. This is analogous to the typical input used in CNNs, a three channel (RGB) image, except each channel corresponds to a single generated spectrogram as opposed to a color. Very subtle changes and patterns in the airway pressure and flow channels can be more readily apparent in their spectral representation than in their raw waveforms. CNNs, which are state-of-the-art in image processing, can accurately and efficiently recognize patterns in stacks of spectrograms. This powerful combination of spectrograms and CNNs is what makes our machine learning technique superior to automation-based approaches (i.e. hard coding the rulesets). Further, the technique can be ventilator agnostic.

Analysis Plan: The existing datasets from all 3 institutions will be combined and patients will be randomly assigned to one of three datasets for derivation (50%), validation (25%), and final testing (25%).

Hypothesis a (algorithm development and testing): We anticipate having nearly 1,000,000 breaths for analysis from existing datasets (500,000 training, 250,000

[figure not shown]

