Figure 10: Example of a synchronous breath (a) compared to an asynchronous breath (b) and the spectral tensor conversions for each, with the DC breath highlighted in orange.

validation and 250,000 in the final test set). Our models will first concentrate on DC breaths using the methods described above. Machine learning experts will work with the clinical team to review breaths in the validation set which have been classified as a certain PVA subtype, but which were not labeled the same way by human annotators (using one of 3 gold standard measures of neural effort). We anticipate many of the PVA annotations by the machine learning algorithm will represent “sub-clinical” PVA, where the breaths are representative of a specific type of PVA, but do not meet the threshold determined by the clinical reviewers. Models will be fine-tuned to differentiate “sub-clinical” from more overtly “clinical” PVA. Final performance will be assessed using the test set only once to ensure an unbiased estimate of the ability of the model to discriminate DC breaths and synchronous breaths. The performance of the models will be assessed using AUROC to assess the overall ability of the model to discriminate between DC breaths and other breaths. Additionally, the recall of the model at various levels of Number Needed to Alert (1.01, 1.1, 1.5, 2) will be analyzed to understand the potential clinical utility. Similar analysis will then follow to identify the underlying PVA subtype leading to the DC breath, and finally to identify other forms of asynchrony, independent of whether it results in a DC breath.

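### Asynchrony Aim 3 pools three hospitals and reports no performance by hospital, so for subtypes whose rates differ strongly between hospitals the pooled AUROC can partly reward recognising the hospital.

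*Combined protocol and SAP*

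**What the plan says.** Protocol section H, Specific Aim 3, Analysis Plan: "The existing datasets from all 3 institutions will be combined and patients will be randomly assigned to one of three datasets", in proportions 50/25/25 for derivation, validation and final testing. Stratification by hospital is not mentioned.

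Hypothesis a sets the order of work and the measures. On the first target: "Our models will first concentrate on DC breaths using the methods described above". Performance is "assessed using AUROC to assess the overall ability of the model to discriminate between DC breaths and other breaths", and in addition "the recall of the model at various levels of Number Needed to Alert (1.01, 1.1, 1.5, 2) will be analyzed". The same approach is then applied to the subtype behind each double-cycled (DC) breath and "finally to identify other forms of asynchrony, independent of whether it results in a DC breath". The test set is used once. Hypothesis b adds alerts over windows of breaths, with a false-alarm goal such as under 5%.

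No result by hospital and no held-out hospital is described. The Summary and Rationale states that each hospital has its own measure of neural effort: esophageal pressure for REDvent, Edi at St. Justine, sEMG at Beatrix. The Aim 1 Preliminary Data acknowledge that subtypes differ with institution, measurement technique and disease state.

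**The concern.** Hospital, labelling sensor and case mix are completely confounded in the pooled data. A pooled AUROC compares every positive breath with every negative breath, including pairs from different hospitals. If a subtype is common at one hospital and rare at another, a network gains on the cross-hospital pairs merely by picking up which hospital a waveform comes from. The inputs are only flow and airway pressure, but the protocol argues that its spectral method brings out very subtle patterns in them. Those could include equipment or practice signatures.

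At stake is what the final test figure means. A bedside user works inside one hospital and needs to know how well asynchronous breaths are separated from others there. A pooled figure can exceed that, most of all for a mediocre classifier.

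**Working it through.** **The protocol's own figure.** Aim 1, Sample Size and Power: 0.03 × 1,000,000 = 30,000 DC breaths, and 0.70 × 371 = 259.7, or 260 patients. Both reproduce.

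**Inputs.**
- Children: 235 REDvent (Aim 2, Sample Size and Power), 62 St. Justine and 74 Beatrix (Aim 1 Preliminary Data). 235 + 62 + 74 = 371, the protocol's total.
- Ineffective triggering, Beatrix: stated as 68%. This exceeds the 33% of breaths that were asynchronous, so it must be a share of those: 0.68 × 0.33 = 22.4% of breaths.
- Ineffective triggering, St. Justine: 10%, read as a share of all breaths.
- Ineffective triggering, REDvent: not listed. For that cohort "28.7% of breaths had some form of asynchrony", and the listed subtypes sum to 13.8 + 7.4 + 5.1 + 1.9 = 28.2%, leaving 0.5%. I assume 0.5%, and up to 1.9% (the rarest listed subtype).
- DC: 3% REDvent, 1% St. Justine, 4% Beatrix.
- Breaths per hospital: not given. I assume shares in proportion to children, equal shares, or REDvent-heavy shares (600/62/74).

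**Hospital-only score.** AUROC = Σ over hospitals i, j of (share of positives from i) × (share of negatives from j) × (1 if rate i > rate j, ½ if i = j, 0 otherwise).

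With shares 235/62/74 and rates 0.5%, 10% and 22.4%, positives divide 0.049/0.259/0.692 and negatives 0.674/0.161/0.165 (REDvent/St. Justine/Beatrix).
- Beatrix positives against the other two: 0.692 × (0.674 + 0.161) = 0.578
- St. Justine positives against REDvent: 0.259 × 0.674 = 0.174
- Ties: ½ × (0.049 × 0.674 + 0.259 × 0.161 + 0.692 × 0.165) = 0.095
- Sum: 0.847. Without breath-level information the value should be 0.50.

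**A classifier with real skill.** Assume scores N(0,1) for negatives and N(d,1) for positives within every hospital, d = √2 × Φ⁻¹(within-hospital AUROC), and a network that also uses each hospital's base rate. A pair from hospitals i and j is then ordered correctly with probability Φ[(d² + logit p_i − logit p_j)/(d√2)], weighted as above.

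Ineffective triggering:

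| Breath shares | REDvent rate | Hospital-only | Pooled if within = 0.80 | Pooled if within = 0.90 |
|---|---|---|---|---|
| By children | 0.5% | 0.847 | 0.921 | 0.957 |
| By children | 1.9% | 0.784 | 0.883 | 0.937 |
| Equal | 0.5% | 0.749 | 0.877 | 0.936 |
| Equal | 1.9% | 0.725 | 0.859 | 0.926 |
| 600/62/74 | 0.5% | 0.878 | 0.937 | 0.965 |
| 600/62/74 | 1.9% | 0.765 | 0.880 | 0.936 |

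DC over the same shares: hospital-only 0.54 to 0.63; a within-hospital 0.90 becomes 0.90 to 0.91; 0.984 becomes 0.984 to 0.985.

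**Other readings.** If REDvent supplied only 10% of breaths (10/45/45), the hospital-only value would be about 0.66 at a REDvent rate of 0.5%. If St. Justine's 10% were a share of asynchronous breaths (2.7% of all breaths), it would be 0.87 by children and 0.81 with equal shares, again at 0.5%.

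**Recall at NNA.** The best positive predictive value of a hospital-only score for ineffective triggering is 22.4%, so NNA = 1/0.224 = 4.5. The planned levels stop at 2, so its recall is zero at all four.

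**The case against.** A reader might infer that the classifier is judged on a single AUROC that a network with no skill could nearly satisfy. The documents do not support that.

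- **AUROC is not the only measure.** Recall at four NNA levels is planned, and a pure hospital shortcut fails all four. Window-level alerts follow. This stands. Pooled recall is nevertheless not a result for any one hospital, because NNA depends on prevalence and DC prevalence runs from 1% to 4%.
- **Overall rates are close.** Any asynchrony is 28.7%, 33% and 27%, and the protocol calls DC rates similar. This stands: the strong differences are between subtypes.
- **The large numbers concern a last-step target.** Ineffective triggering is not named in Aim 3. It falls under the other forms of asynchrony examined after DC and its causes. This stands and limits the point to those later analyses.
- **The preliminary AUC of 0.984 might seem suspect.** It is not: those models were trained and tested on REDvent patients only, so pooling cannot have inflated it.
- **Definitions will be harmonised.** Aim 1 requires kappa above 0.8 by subtype and sensor, while the rates used here come before that step, so differences may shrink. This stands in part. Kappa measures agreement between readers; it does not equalise rates between hospitals, and the protocol also attributes the differences to disease state.
- **A random split by patient already tests new patients.** Correct, and Hypothesis b promises internal validation only. The absence of a held-out hospital is therefore not a defect in itself.

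**Conclusion.** The point holds for the later subtype analyses of a secondary aim. Pooled AUROC can overstate within-hospital discrimination where rates differ strongly by hospital, and no planned output would show it. For ineffective triggering the hospital-only value is about 0.73 to 0.88, an upper-bound illustration because it supposes perfect hospital recognition. The more relevant figures are those for a classifier with some skill: 0.80 reported as about 0.86 to 0.94, and 0.90 as about 0.93 to 0.97. For DC the effect is small, and negligible near 0.98.

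These sizes rest on an inferred REDvent rate, assumed breath shares, a binormal score with equal skill at all hospitals, full use of hospital base rates, and rates that precede harmonisation. The primary trial analysis is not affected. This is a cheap improvement.

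**What to change.** In section H, Aim 3, Analysis Plan, stratify the 50/25/25 split by hospital. Under Hypothesis a, make the performance measures AUROC and recall at each NNA level within each hospital, and their average over hospitals, with intervals from bootstrapping children rather than breaths. Keep the pooled AUROC as descriptive. A hospital-only score then gives exactly 0.50 for every subtype. Because the test set is used once, the wording should be settled before that use.

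A leave-one-hospital-out run is an optional sensitivity analysis, needed only if transfer to an unseen hospital is to be claimed. Each hospital has its own labelling sensor, so such a run would mix site transfer with a change of label source.

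The cost is revised wording and some computing; three refits are needed only for the optional run. The downsides are that reported AUROCs may be lower and that estimates at the two smaller hospitals will be imprecise: a quarter of 62 and of 74 children is 15.5 and 18.5, so about 16 to 19 test children each.

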Analysis of PVA subtypes leading to DC breaths, and identification of risk factors: Each dataset contains detailed diagnostic data, demographics, ventilator settings, and medication data. Using data from existing datasets, all patients and all days of ventilation will be analyzed to describe the frequency of PVA subtypes leading to DC breaths. For each DC breath (anticipated 3% of all breaths), one of three underlying PVA subtypes will be annotated (Reverse Trigger, Flow Undershoot/Premature Termination, Auto-trigger, Figure 4). Flow undershoot and premature termination represent the same physiologic concepts of inadequate ventilator support, so they will be combined for analysis of DC breaths. We anticipate that RT and Flow Undershoot/Premature Termination will continue to comprise $> 95\%$ of the causes of DC and will be the primary focus of analysis. We will evaluate ventilator and patient specific risk factors for PVA subtypes which lead to DC.

Sample Size and Power: From existing datasets, we are anticipating having over 1,000,000 breaths for analysis, from 371 patients, with more than 1,000 patient days. Based on our preliminary data, 3% of breaths are DC, and 70% of patients have at least one episode of DC. This should give us a minimum of 30,000 DC breaths from 260 patients. This will permit inclusion of dozens of variables in the risk factor analyses, although we anticipate between 3-5 in each model. Analysis will be conducted on the breath and on the patient level.

The goal of the breath level model is to understand why DC occurs when a specific PVA subtype is present. We will create two prediction models, one to identify risk factors for DC related to RT and one to identify DC related to flow undershoot/premature termination. Variables considered in the breath-by-breath model include parameters with biological plausibility to be in the causal pathway for the PVA subtype or DC including ventilator mode (including NAVA), respiratory rate, ventilator rate (RRvent), spontaneous or neural respiratory rate (RRneural) and neural

Asynchrony subtypes leading to Double Cycled Breaths

[figure not shown]

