Preclinical data confirms that PVA leads to VIDD and VILI. Several mechanistic studies, including published analysis by our group, confirms that PVA leads to VIDD and VILI.⁶⁴⁻⁶⁷ In a rabbit model, we identified that VIDD was reduced with a ventilation strategy promoting spontaneous breathing using pressure support ventilation compared to controlled ventilation, but that this injury could be further reduced with Neutrally Adjusted Ventilatory Assist (NAVA) by reducing the rates of PVA.⁶⁷ Interestingly, diaphragmatic injury from over-assistance myotrauma (common during controlled ventilation without spontaneous breathing) resulted in atrophy, while diaphragmatic injury from PVA was mediated by sarcomere disruption. There was a dose response relationship between Asynchrony Index and fraction of sarcomere disruptions in the diaphragm (Figure 6). Both

PVA subtypes are associated with clinical and mechanistic outcomes. Preliminary analysis from 65 patients in the REDvent dataset evaluated the association between PVA rates on the first day of spontaneous breathing and outcomes. While the sample size from this preliminary data is under-powered, it highlights the potential magnitude of effect we may see with the larger sample size in this application. We have not conducted group-based comparison (REDvent versus control), as study investigators need to remain blinded to group-based analyses until completion of REDvent (Dec 2023). Flow undershoot represents inadequate support on the ventilator and not surprisingly was associated with longer length of ventilation ($p < 0.05$, Figure 7a) perhaps through hypertrophy of the diaphragm (Dte increased), although this analysis is limited by sample size with only 7/65 patients in the hypertrophy group ($p = 0.4$, Figure 7b). Moreover, patients who had DC breaths had higher rates of delirium, as measured by the Cornell Assessment of Pediatric Delirium (CAPD) screener ($p < 0.01$, Figure 7c). This may relate to agitation from PVA which manifests with the same symptoms as delirium, or it may be that delirium itself makes it harder for patients to synchronize with the ventilator. Children with reverse trigger received higher doses of opioids ($p < 0.01$, Figure 7d), which re-enforces that alteration of neural respiratory rate (suppressed with opioids) may make RT more common.

[figure not shown]

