Figure 7: (a, top left) Length of ventilation (days) is higher in children with flow undershoot forms of PVA when spontaneous breathing does not occur until after the 3rd day of ventilation (b, top right) Diaphragm hypertrophy may be more likely to occur in children with flow-undershoot forms of PVA (c, bottom left) Delirium scores are higher in children with high rates of Double Cycled breaths. (d, bottom right) Reverse Trigger patients receive higher doses of opioids.

Methods and Analysis Hypothesis A: Here we seek to test whether the REDvent intervention results in different rates and subtypes of PVA than usual care. This type of analysis is perfectly suited to secondary analysis of a randomized trial, where the intervention is striving to promote more spontaneous breathing with a downstream influence on PVA. This would not be possible to do with an observational cohort, because of inherent selection bias in which patients are permitted to have more spontaneous breathing. We believe the forms of asynchrony which lead to DC breaths (flow undershoot/premature cycling) and reverse trigger may be different in REDvent versus control patients. This aim will use all available patients with spontaneous breathing in the REDvent dataset (expected 235). For each patient day with spontaneous breathing, PVA subtypes will be analyzed. The proportion of breaths which fall into a particular PVA subtype will be expressed in addition to global asynchrony index, calculated as the total number of asynchronous breaths over the total number of breaths.³⁰ Because rates of PVA may vary from day to day, analysis will focus on both an area under the curve of PVA over all days (calculated as the total number of asynchronous breaths over the total number of breaths available for analysis) in addition

to the highest rate of PVA on any day for each patient, by PVA subtype. PVA and PVA subtype rates per patient will be expressed as a continuous variable and compared between REDvent and usual care patients using a Mann Whitney U test given it is not expected to be normally distributed. PVA subtypes which are different between REDvent and control patients will be considered for mediation analysis (below).

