Univariable analysis will focus on the relationship between the PVA variables above and clinical and mechanistic outcomes. Nearly all the variables of interest are continuous, so analyses will focus on strength of association and dose response. Nonparametric or parametric correlations will explore the relationships between continuous variables. The primary clinical outcome of length of ventilation after the first day of spontaneous breathing will be modelled with a competing risk regression to look at time to extubation against the competing risk of death. This type of model is necessary rather than traditional survival analysis or linear regression because both death and prolonged ventilation are undesired outcomes, and some proportion of children (likely 5-10%) will die even after the first day of spontaneous breathing. We have successfully used this framework in previous investigations.⁶⁸⁻⁷² We will then add in variables which may confound the relationship between PVA and clinical outcomes including demographic factors (age, co-morbidities), severity of initial lung injury, diagnostic data and medications. Similar analyses will be repeated all clinical and mechanistic outcomes. For mechanistic analysis (table 2), within each of the proposed mechanisms (VILI, VIDD, Delirium), the variable with the strongest association with PVA (or its subtype) will be included as the outcome variable.

Specific Aim 3) To develop and test a clinical decision support system using machine learning techniques to automatically identify common forms of PVA in children.

Hypothesis: (a) Machine learning models using waveforms available on all mechanical ventilators will accurately identify PVA subtypes compared to gold standard annotations which include measures of neural drive. (b) Algorithms can be optimized for high sensitivity and low false alert rates to identify children with frequent PVA.

Preliminary Data

Machine learning methods can detect DC breaths and the PVA subtypes leading to DC. We have been developing a machine learning framework using Spectral Analysis with a Convolutional Neural Network to detect PVA subtypes. Details about the methods used (and intend to employ here) are described below. Preliminary models were trained on 34, validated on 13 and tested on 18 patients from the REDvent dataset.

[figure not shown]

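### The Aim 3 asynchrony test set will include children already used to build and test the preliminary network, so the claim of an unbiased accuracy estimate is not secured

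*Combined protocol and SAP*

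**What the plan says.** All of this is in section H of the amended protocol, on patient-ventilator asynchrony.

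- **Earlier network.** Aim 3, Preliminary Data: "Preliminary models were trained on 34, validated on 13 and tested on 18 patients from the REDvent dataset". The same section says the methods used there are the ones to be employed again. It also describes expert re-review of several files in which the model disagreed with the annotators, and plans further training to adjust thresholds.
- **New split.** Aim 3, Analysis Plan: the datasets of the three institutions are combined and "patients will be randomly assigned to one of three datasets for derivation (50%), validation (25%), and final testing (25" per cent).
- **Claim.** Aim 3, Hypothesis a: "Final performance will be assessed using the test set only once to ensure an unbiased estimate of the ability of the model" to separate double-cycled from synchronous breaths.
- **Earlier associations.** Aim 2, Preliminary Data: "Preliminary analysis from 65 patients in the REDvent dataset evaluated the association between PVA rates on the first day of spontaneous breathing and outcomes". It reports flow undershoot with longer ventilation (p<0.05), double cycling with delirium (p<0.01) and reverse trigger with opioid dose (p<0.01).
- **Planned population.** Aim 2, Hypothesis A methods: "This aim will use all available patients with spontaneous breathing in the REDvent dataset (expected 235"). The opening summary of section H likewise includes every child enrolled in REDvent.

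Nowhere are the 65 excluded, fixed in one part of the split, or analysed separately.

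**The concern.** A test set gives an honest accuracy estimate only if nothing learned from its members shaped the model. Opening it once is necessary but not sufficient, because the members must also be new. Here the preliminary work used 65 REDvent children, and its methods, and possibly its thresholds or weights, are carried into the planned work. A random re-split then returns some of those children to the test set. Hypothesis b adds to the point: it wants the alert system to mimic use on a patient not seen before.

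The reported discrimination and alert burden would be the basis for offering a bedside tool, so the reader needs to know that they come from unseen children. A related but lesser issue arises in Aim 2 Hypothesis B, where associations already observed in 65 children will be estimated again in a sample that contains them.

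**Working it through.** **1. Who is in the pool.** The inputs are 235 REDvent children (Aim 2, Hypothesis A methods), "In a mixed cohort of 74 children at Beatrix" and "mixed cohort of 62 children at St. Justine" (both Aim 1, Preliminary Data).

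235 + 74 + 62 = 371

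This reproduces the stated total exactly ("from 371 patients, with more than 1,000 patient days", Aim 1, Sample Size and Power). The total therefore counts all expected REDvent children and leaves nobody out. The preliminary network used 34 + 13 + 18 = 65 of them. These 65 cannot be a separate group on top of the 235, because 235 + 65 = 300 exceeds 276, the upper end of the enrolment target (final SAP, January 2023 entry). Without them, 371 − 65 = 306 children remain, of whom 235 − 65 = 170 are from REDvent.

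**2. Overlap with the new test set.** The test set has 0.25 × 371 = 92.75, so 93, children. If K children were used before, the number drawn is hypergeometric with mean 93 × K / 371.

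| Previously used children | K | Expected in test set | Share of test set | 95% range |
|---|---|---|---|---|
| All | 65 | 16.3 | 17.5% | 10 to 23 |
| Trained or validated the network | 47 | 11.8 | 12.7% | 7 to 17 |
| Earlier test set | 18 | 4.5 | 4.9% | 1 to 8 |

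The chance that none of the 65 is drawn is about 8 × 10⁻¹⁰. That shows overlap is practically certain; it says nothing about the size of any bias.

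**3. Size of the bias.** The plan does not say whether weights, architecture or thresholds carry over, so this can only be illustrated. Assume the AUC in previously used children is too high by 0.01 to 0.05, and that the pooled AUC moves roughly in proportion to their share.

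- Low end: (47/371) × 0.01 = 0.0013
- High end: (65/371) × 0.05 = 0.0088

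Both inflation values are assumptions, not figures from the plan.

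**4. The split after the change.** Derivation takes 186 children (65 used plus 121 new), validation 93 and test 92. The new children needed are 121 + 93 + 92 = 306, which is exactly the number available. With a test set of 93 in proportion to hospital, REDvent supplies 93 × 235/371 ≈ 59 children, drawn from 170 unseen. The other two hospitals supply about 93 × 74/371 ≈ 18.5 and 93 × 62/371 ≈ 15.5. The test set keeps its size and hospital mix.

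**5. Hypothesis B.** The 65 are 65/235 = 27.7% of the expected sample. An estimate from the other 170 has an interval wider by √(235/170) = 1.18, about 18%. For a correlation of 0.3 (the value the plan assumes in its mediation sample size), power by Fisher's z is 0.98 with 170 children and 0.997 with 235. Two-sided 0.05 is assumed, since section H states no alpha.

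**The case against.** Several points on the other side stand.

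- The new split is by patient, uses three hospitals and starts from definitions that are to be harmonised afresh. If the network is refitted from scratch, only indirect optimism from earlier design choices remains. The re-review of disagreements is not said to have changed any labels. The 18 children of the earlier test set did not train or tune anything.
- A reader might infer that Hypothesis B p-values are heavily inflated. Writing Z(all) = √(65/235)·Z(first 65) + √(170/235)·Z(rest), a null association already at p<0.05 in the 65 reaches p<0.05 in all 235 with probability 0.20; one already at p<0.01 does so with probability 0.31. These figures hold only given a true null, an already significant pilot and the same statistic both times. They are not the error rate of the planned tests, which would keep their level if they were to be run anyway. The plan also rests Hypothesis B on adult and preclinical data, says it will mainly establish associations, and does not call the analysis confirmatory.
- The statistic is not always the same. The flow undershoot finding concerned first-day asynchrony and, by the Figure 7a caption, children with no spontaneous breathing until after day 3. The planned primary outcome is ventilation after the first day of spontaneous breathing, in a competing-risk model. Table 2 of section H does not pair double cycling with delirium. Only reverse trigger with opioid dose is a clean match.
- A reader might extend the point to Hypothesis A. The plan says no comparison of REDvent with control was made in the 65, so that analysis is untouched by this route.

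What these points leave standing is the explicit claim of unbiasedness for a test set that will not consist of unseen children.

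**Conclusion.** The point holds for the Aim 3 test set. About one test child in six (16 of 93) will have been used before under the plan as written, so single use alone does not deliver the property claimed. The amount of optimism cannot be stated from the documents: it depends on what carries over, and it may be small.

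The overlap figures assume that Aim 3 splits the same 371 children counted in Aim 1, that assignment is simple random, and that all 65 lie within the 235. For Hypothesis B the documents support a call for disclosure and a sensitivity analysis, not a finding that its tests are invalid.

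That the network's 65 and the association set's 65 are the same children is an inference from equal counts and a common source. The breath counts do not confirm it: Aim 1 gives 54,284 breaths in 65 patients, while Aim 3 gives more than 49,000 in 18 patients and 10,326 in 13, together above 59,326. Neither part of the point needs the two sets to coincide. The trial's own primary outcome is not affected.

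**What to change.** **Aim 3.** State in the Analysis Plan that the 65 REDvent children used in the preliminary network are assigned to derivation or validation, and that the test set of about 93 is drawn at random, stratified by hospital, from the roughly 306 unseen children. Also state whether any preliminary weights, architecture choices or thresholds are retained. This needs no new data and leaves the test set at its planned size. The small cost is that 170 rather than 235 REDvent children are eligible for it.

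**Aim 2, Hypothesis B.** Disclose that flow undershoot with length of ventilation, double cycling with delirium, and reverse trigger with opioid dose were already examined in 65 of the expected 235 children. Keep the full-sample analysis, and report these three associations also without the 65 as a sensitivity analysis. The cost is one extra set of estimates, with intervals about 18% wider. Hypothesis A needs no change.
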